1. SYNOPSIS

Study Name and Unique Number	Clinical Study to Evaluate the Safety and Performance of the Calcivis System for Identifying Active Demineralization on Tooth Surfaces – CAL-02-2014
Study Objectives	
Primary Objectives
 
Performance of the Calcivis System, as measured by the presence or absence of elevated luminescence on the surface of the tooth determined from intra-oral image mapping of that surface (with or without a visible lesion).
 
Safety of the Calcivis System, as measured by the collection of all adverse events
 
The Secondary Objective of the study is:
 
To assess the usefulness of the Calcivis System images, as a communication tool between patient and dentist, as measured by Questionnaires and / or Patient Visual Analogue Scales.

Study Device - Intended Use and Indications	
The Calcivis Caries Activity Imaging System comprises:
 
Calcivis Imaging Kit - Administration and Imaging device
 
Consists of:
 
 ▪ Calcivis Intra-oral Imaging Device ▪ Device cradle ▪ Calcivis (Imaging) Software on DVD/CD ▪ Calcivis Instruction Manual 
Accessory - Calcivis Disclosing Solution Kit – single use
 
Consists of:
 
 ▪ Calcivis Disclosing Solution (Freeze dried in vials) ▪ Water for reconstitution ▪ Syringe ▪ Needleless adaptors 
and / or
 
Accessory – Calcivis Disclosing Solution (Photprotein) Kit - Multi-use
 
Consists of:
 
 • Calcivis Photoprotein (Disclosing Solution) - Freeze dried in a vial • Vial of Calcivis Diluent (Water for reconstitution) • Single-use Device Syringes (sterile prior to opening) • Vial Adaptors x 2 
Accessory – Calcivis Application Kit
 
Consists of:
 
 • Single-use Calcivis Applicators x10 
The Calcivis Caries Activity Imaging System is intended to be used by dental healthcare professionals on patients (6 years and older) with, or at risk of developing, caries lesions on coronal tooth surfaces.
 
The Calcivis Caries Activity Imaging System is indicated for use to provide images of active demineralization on tooth surfaces, as an aid to the assessment and diagnosis of caries lesions.

Study Design	Prospective, multi-site, non-randomised, post-approval clinical study

Patient Population:	Eligible patients will be recruited from routine, general dental practices who have one unrestored, accessible, free smooth buccal surface on a canine or incisor, away from the gingival surface, identified with no visible lesion (coded ICDAS 0), and / or one unrestored, accessible, erupting or erupted molar or pre-molar with a visible lesion identified (coded ICDAS 2 or 3) in a plaque stagnation area.
Inclusion and Exclusion Criteria	
Inclusion criteria
 
 1. Patient must be \geq 6 years old 2. Patient must have one unrestored, accessible, free smooth buccal surface on a canine or incisor, away from the gingival surface identified with no visible lesion (coded ICDAS 0) – ref. table on page 27 and / or 3. Patient must have one unrestored, accessible, erupting or erupted molar or pre-molar with a visible lesion identified (coded ICDAS 2 or 3) in a plaque stagnation area – ref. table on page 27 4. Patient and / or parent or guardian must be willing and able to give written informed consent 5. Patient and / or parent or guardian must be willing and able to adhere to study schedule 
Exclusion criteria
 
 1. Any Patient with recent tooth bleaching (within previous two weeks of imaging with the Calcivis System) 2. Any Patient having on-going re-mineralization treatment including, but not limited to high concentration prescription fluoride toothpaste 3. Any patient with a fixed orthodontic appliance 4. Any patient currently taking part in a clinical research study, or has taken part in a clinical research study in the previous three months 5. Pregnant and / or nursing mothers

Statistical Rationale	
The study will assess the agreement between the Calcivis System and dentist rating of suitable teeth into two categories: 'no visible lesions' or 'active lesions'. Based on previous study data and expert opinion, 'No visible lesions' are expected to correspond to 'no luminescence' in at least 70% of cases. Similarly, 'active lesions' are expected to correspond to 'luminescence' in at least 70% of cases.
 
For the purpose of sample size calculations, the percentage agreement for each of the two categories are jointly considered as measures of agreement. That is, both measures will need to show statistically significant agreement for the study to be considered successful.
 
The study is sized to provide at least 90% power to reject the null hypothesis of chance agreement (50%). Statistical hypothesis tests will be 1-sided and conducted at the 2.5% significance level.
 
This requires a minimum of 81 evaluable teeth of each category.

Number of Patients / Investigator	
A minimum of 17 and a maximum of 18 teeth from each tooth population are required from each Investigator (a total of 85 to 90 teeth from each tooth population).
 
Therefore per Investigator - if all patients have one of each tooth population, a minimum of 17 patients per Investigator will be recruited and if all patients only have one of each tooth population, a maximum of 36 patients will be recruited.
 
Therefore the number of patients recruited to the study will range from 85 to 180.

Number of Sites	Four (4)

Sites and Investigators	
Site 01: [name] (Chief Investigator) Downie, Harper & Shanks Dental Practice [name] [name] Scotland [contact]
 
[name] (Investigator) Downie, Harper & Shanks Dental Practice [name] [name] Scotland [contact]
 
Site 03: [name] (Investigator) Bathgate Smile Centre [name] [name] West Lothian Scotland [contact]
 
Site 04: [name] (Investigator) Marchmont Periodontics [name] [name] Scotland [contact]
 
Site 05: [name] (Investigator) Bosco Dental Studio [name] [name] Scotland [contact]

Duration of Procedure	Preparation for Imaging is expected to take approximately one minute per tooth with imaging itself taking less than one second. All eligible teeth per patient will be imaged at the same dental visit
Follow-Up	7 to 14 days post imaging

Duration of Study	The overall study period is expected to take 10 months - 3 months for Ethics Committee and R & D approval, 2 to 3 months for recruitment and study procedures, and 4 months for final follow up, data collection and analysis.
Regulatory Status	The Calcivis System is a Class IIa Medical Device which is CE marked in the EU.

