In May 2014, the first formal Post-Approval Clinical Study was performed in adults (16 to 25 yrs old) using the advanced prototype Calcivis System. The Primary Objectives of the study were to assess the Performance and Safety of the Calcivis System, and the Secondary Objective was to assess user experience with the Calcivis System (both User and Patient). A total of 42 patients were recruited to the study from three UK, General Dental Practices, to obtain a total of 31 evaluable patients. Eligible patients were those with interpretable images of both a tooth with no visible lesion identified (ICDAS Code 0) and a tooth with a suspected visible lesion identified (ICDAS Code 1, 2 or 3). Images from 11 patients were not eligible for interpretation due to confounding factors including ambient light ingress, gross saliva contamination and poor disclosing solution coverage on the tooth surface. All these issues have been addressed in the design phase for the new commercial Calcivis System which is the subject of this study.

All 42 patients were included in the Safety Population – two adverse events were recorded – bleeding gums and slight gum abrasion – both were device-related, non-serious and asymptomatic to the patients with no action required. One other adverse event was recorded as a device deficiency when the device jammed and did not dispense fluid.

31 patients were included in the Agreement Population – analysis of the level of agreement between the ICDAS scores and elevated luminescence, (Y/N) as defined by the Investigators.

For the primary study objectives, the study results concluded that: -

1. The Calcivis System was safe in clinical use as determined by the low number and minor nature of the adverse events recorded.

2. Analysis of the overall level of agreement between elevated luminescence and the presence of lesions predicated as active by the Investigators showed agreement in 47 of the 65 teeth imaged (72.3 %) which was statistically significant, not due to chance and above the expected level of 70%.

(Of the 31 teeth identified by the Investigators with no visible lesions, 26 showed no elevated luminescence using the Calcivis System – corresponding to a negative percentage agreement of 83.9%. Of the 34 teeth with visible lesions identified by the Investigators, 21 showed elevated luminescence using the Calcivis System – corresponding to a positive percentage agreement of 61.8%).

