7.2 Patient Selection and Confidentiality

To ensure poolability of the data from each Investigator, up to 36 patients may be recruited to the study (to obtain a minimum of 17 evaluable images of each tooth population) by five Investigators from four general dental practices. Patients will be identified and selected according to the Inclusion / Exclusion criteria listed below. All patients and / or parent or guardian must provide written informed consent and be willing to adhere to the study schedule, before being entered in to the study.

Patients will be encouraged to complete both Study Visits, however, patients are free to withdraw Consent at any time, irrespective of their initial consent.

Patients may also be withdrawn from the study by the Investigator on the grounds of safety. Any patients who withdraw or are withdrawn from the study will be replaced.

All patients recruited to the study will be identified by a unique study number, comprising the site number and a patient number, to allow any data collected on them to be anonymized. The investigator will maintain a confidential patient identification list of all patients enrolled in the study (by name and patient number). The list will be maintained at the site and will not be retrieved by the Sponsor. There is no randomization required in this clinical study.

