10. STATISTICAL ANALYSIS

10.1 Sample size

The study will assess the agreement between the Calcivis System and dentist rating of suitable teeth in two teeth populations: 'no visible lesions', and 'active lesions'. Based on previous study data and expert opinion, 'No visible lesions' are expected to correspond to 'no luminescence' according to the Calcivis system in at least 70% of cases. Similarly, 'active lesions' are also expected to correspond to 'luminescence' in at least 70% of cases.

Subjects will provide no more than one tooth of each tooth population. The study sample size is calculated in terms of the number of teeth of each tooth population required. The number of subjects required is then *at most* the total number of teeth required.

For the purpose of sample size calculations, the percentage agreement for each of the two tooth populations are jointly considered as measures of agreement. That is, the study will be deemed a success if the percentage agreement in both of the tooth status populations is statistically significant at the 2.5% level when compared to chance agreement (50%).

Expressed in terms of hypothesis tests, the null and alternative hypotheses are:

$$H_0: p_{a,i}=0.5 \text{ vs. } H_1: p_{a,i}>0.5 \text{ for each tooth status population } i$$

where $p_{a,i}$ is the percentage agreement in tooth status population i .

To achieve at least 90% power overall, a power of 94.9% has been used for each tooth status population individually. The planned method of analysis is an exact binomial test and this has been used to derive a required sample size of 81 for each of the tooth status populations. This is the first sample size after which all subsequent sample sizes provide at least 94.9% power.

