## 4.0 Study Design

This is a prospective, multi-site, non-randomised, post-approval clinical study to assess the use of the Calcivis System for assessing active demineralization on tooth surfaces of teeth in patients 6 years and older. This post-approval clinical study will be conducted under the controlled conditions of this clinical study plan, on eligible patients, in a general dental practice setting.

The prevalence of active lesions found on the occlusal surfaces of erupting teeth is affected by the erupting stage status of the teeth – with the prevalence of active lesions greater in the earlier eruption stages.

As a result of these and similar findings the choice of teeth for identifying visible lesions which are potentially ‘active’ has been limited to erupting and erupted molars and premolars.

To ensure poolability of the data from each Investigator, up to 36 patients may be recruited to the study (to obtain a minimum of 17 evaluable images of each tooth population) by five Investigators from four general dental practices. All patients and / or parent or guardian must provide written informed consent and be willing to adhere to the study schedule, before being entered in to the study.

Patients will be encouraged to complete two Study Visits, however, patients are free to withdraw consent at any time, irrespective of their initial consent. Patients may also be withdrawn from the study by the Investigator on the grounds of safety. Any patients who withdraw or are withdrawn from the study will be replaced.

The overall study period is expected to take 10 months - 3 months for Ethics Committee and National Health Service Research and Development approval, 2 to 3 months for recruitment and study procedures, and 4 months for final follow up, data collection and analysis.

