### ***9.2 Missing Data***

Missing data arising from teeth where the Calcivis System assessment is uninterpretable for reasons that are thought unrelated to the assessment outcome (image out of focus, ambient light ingress) will not be imputed. Otherwise missing data will be considered as a disagreement in the calculation of agreement. Secondary analyses based on imputing all missing data as a disagreement will be conducted, if appropriate.

Otherwise missing data will not be imputed.

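### The 36-patient ceiling in Protocol 7.2 and SAP 4.0 contradicts the synopsis, and the stated 90% joint power ignores unreadable teeth that the SAP scores as disagreements

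*Protocol*

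**What the plan says.** **Numbers to recruit.** The Protocol synopsis requires 81 evaluable teeth in each class (no visible lesion; active lesion). For each Investigator it says "A minimum of 17 and a maximum of 18 teeth from each tooth population are required from each Investigator", which it totals as 85 to 90 teeth per class. It derives 17 patients per Investigator if all patients have one of each class, and then says "if all patients only have one of each tooth population, a maximum of 36 patients will be recruited". The study total is given as 85 to 180 patients.

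Protocol 7.2 says "up to 36 patients may be recruited to the study (to obtain a minimum of 17 evaluable images of each tooth population", followed by the statement that five Investigators at four practices will do this. SAP 4.0 repeats it: "up to 36 patients may be recruited to the study". Protocol 8.2 and SAP 5.2 stop each Investigator's recruitment once at least 17 evaluable images per class are obtained, and allow one repeat image of a tooth.

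**Power.** Protocol 10.1 states: "To achieve at least 90% power overall, a power of 94.9% has been used for each tooth status population individually". It assumes 70% agreement against a null of 50% and an exact binomial test. The synopsis adds: "Statistical hypothesis tests will be 1-sided and conducted at the 2.5% significance level". SAP 6.0 carries the same calculation.

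**Unreadable images.** SAP 8.2 puts every tooth with a dentist ICDAS score into the Agreement Population. SAP 9.2 leaves out images lost to poor focus or ambient light, then says: "Otherwise missing data will be considered as a disagreement in the calculation of agreement". On the previous study, Protocol 5.7 reports: "Images from 11 patients were not eligible for interpretation due to confounding factors including ambient light ingress, gross saliva contamination", and adds poor solution coverage as a third cause. It says the new design has dealt with these issues, but gives no failure rate for the new device.

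**The concern.** There are two separate problems.

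First, the governing text gives two patient ceilings that differ fivefold. Each patient supplies at most one tooth per class, so 36 patients in the whole study cannot produce 81 teeth in either class. The synopsis adds to the confusion by attaching both 17 and 36 patients to the same condition. Seventeen follows if each patient supplies both kinds of tooth. Thirty-six follows only if each supplies a single tooth.

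Second, the sample size and the analysis use different denominators. The sample size counts evaluable teeth. The primary analysis also keeps teeth that could not be read for a reason outside the two listed in SAP 9.2, and scores them against the device. Saliva contamination and poor coverage, both seen in the previous study, are outside that list. Each such tooth enlarges the denominator and can never count as agreement, so the power of the planned analysis may be below the figure stated for it.

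**Working it through.** **Inputs.** One-sided alpha 0.025 in each class; null agreement 0.50; expected agreement 0.70; exact binomial test; both classes must succeed (Protocol synopsis and 10.1, SAP 6.0). Joint power is taken as per-class power squared, which assumes the two classes are independent.

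**Step 1: reproduce the 81.** Let r(n) be the smallest count with P(X ≥ r | n, 0.5) ≤ 0.025. Per-class power is P(X ≥ r(n) | n, 0.7). The per-class target is √0.90 = 0.9487, printed as 94.9%.

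| n per class | r(n) | Exact alpha | Per-class power | Joint power |
|---|---|---|---|---|
| 36 | 25 | 0.0144 | 0.609 | 0.371 |
| 80 | 50 | 0.0165 | 0.941 | 0.886 |
| 81 | 50 | 0.0224 | 0.957 | 0.916 |
| 85 | 53 | 0.0147 | 0.949 | 0.900 |
| 90 | 55 | 0.0223 | 0.973 | 0.946 |

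From n = 81 upwards joint power never falls below 0.90, so the plan's 81 is reproduced. (Against an unrounded 0.9490 the answer would be 86, because n = 85 gives 0.9489. That is rounding only.)

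**Step 2: the 36-patient ceiling.** Thirty-six patients at no more than one tooth per class give at most 36 teeth per class, with joint power 0.609² = 0.37. Per Investigator, 5 × 36 = 180, which is the top of the synopsis range, and 36 single-tooth patients split evenly give 18 + 18 teeth. The synopsis is therefore coherent only if 36 is per Investigator and applies to patients supplying one tooth each.

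**Step 3: unreadable teeth scored as disagreements.** Take 85 evaluable teeth per class (5 × 17, the point at which recruitment may stop) and add k unreadable teeth that SAP 9.2 does not excuse. The denominator is 85 + k, but only the 85 can agree. Per-class power is P(X ≥ r(85 + k) | 85, 0.7).

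| k per class | Denominator | r | Per-class power | Joint power |
|---|---|---|---|---|
| 0 or 1 | 85, 86 | 53 | 0.949 | 0.900 |
| 2 or 3 | 87, 88 | 54 | 0.920 | 0.85 |
| 4 or 5 | 89, 90 | 55 | 0.881 | 0.78 |
| 8 or 9 | 93, 94 | 57 | 0.763 | 0.58 |

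Two failures are 2/87 = 2.3% of the teeth in a class. The last row exceeds 90 teeth, so it can arise only if 17 to 18 counts evaluable rather than imaged teeth.

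**Step 4: unreadable teeth that are excluded.** From 90 imaged teeth, the slack against 81 is 90 − 81 = 9 teeth, or 10%. Losing one tooth in 18 at every Investigator leaves 5 × 17 = 85 teeth, with joint power 0.900. With each of 90 teeth lost independently with probability 0.10 and the rest analysed, joint power averaged over the number remaining is 0.901.

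**The case against.** The strongest reply is that the 36 is plainly a slip. The sentence in 7.2 concerns pooling data from each Investigator, and the synopsis gives both the per-Investigator figure and the 180 total. That is the likely meaning, so 0.37 is the consequence of the literal text, not a forecast. The contradiction still stands in both governing documents.

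A reader might go further and infer that one spare tooth in 18 leaves 81 teeth and 90% power unsecured. The documents do not support that. One in 18 is the slack against the target of 17 per Investigator; against 81 it is 9 in 90, and Step 4 shows that excluded losses of about that size leave joint power near 0.90. Nor do the documents say that 18 caps imaged teeth, and Protocol 7.2 and 8.2 count evaluable images. Patients who supply both teeth also allow more than 18 imaged teeth per class within 36 patients.

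It is also tempting to apply the previous study's loss, 11 of 42 patients (26%), to each tooth here. That figure comes from a prototype, is counted per patient, and required both teeth to be readable. The plan permits a repeat image, says the causes were addressed, and under Protocol 14.8 allows patient numbers to be raised with agreement and ethics approval.

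Finally, not every failure is penalised, since ambient light is on the excused list. That is why Step 3 counts only unexcused failures. How many there will be cannot be known from the documents.

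**Conclusion.** The concern holds in two parts.

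- **Ceiling.** Protocol 7.2 and SAP 4.0 contradict the synopsis, and the synopsis gives the wrong condition for its 36. This rests on the text alone.
- **Power.** The 81 is correctly derived for evaluable teeth, but joint power of at least 90% is not a property of the analysis as planned. At 85 evaluable teeth per class the margin is almost nil (0.9003). Two unexcused unreadable teeth per class bring joint power to 0.85, and four bring it to 0.78. This assumes 70% true agreement in both classes, independence between classes, and equal numbers of failures in each.

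The documents give no basis for saying that 81 teeth will not be reached, or that excluded images threaten the power to any important degree. The number of unexcused failures is unknown, so the table in Step 3 shows sensitivity and does not predict the result.

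**What to change.** - **Protocol 7.2 and SAP 4.0:** write 'up to 36 patients per Investigator (180 in total)'.
- **Synopsis:** make the 36 conditional on 'if every patient provides only one tooth', and state that 17 to 18 counts evaluable teeth.
- **Protocol 10.1 and SAP 6.0:** state that joint power of at least 90% is conditional on at least 81 evaluable teeth per class with no unreadable tooth scored as a disagreement. Then give joint power under the SAP 9.2 rule for a small number of such failures, for example the 0.85 and 0.78 above for two and four per class on top of 85 evaluable teeth.

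The cost is wording in two documents and a less favourable stated power. No extra enrolment and no change to the test is needed.

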2. SCHEDULE OF EVENTS

	Screening	Visit 1			Visit 2	Indendent Review
	Pre-Imaging	Pre- Imaging	Imaging	Post-Imaging	Post-Imaging (7 to 14 days)	
Identification of patients / issue of Patient Information Sheet	X					
Written Informed Consent		X				
Demographics		X				
Inclusion / Exclusion Criteria		X				
Oral Hygiene information		X				
Tooth ID (ICDAS score / activity status) and cleaning		X				
Intra-oral colour photographs – tooth surface only		X				
Calcivis System - Images / disclosing solution / images			X			
Adverse Events (intra-oral colour photograph if relevant)		X	X	X	X	
Image interpretation – Dentist			X			
Image review – Dentist and Patient			X			
Patient Questionnaire / Visual Analogue Scale			X			
User Questionnaire			X			
Second Investigator / Dentist Image Review						X

3. INTRODUCTION

3.1 Background

Dental caries (tooth decay) is a significant clinical and public health problem. Caries is associated with localised demineralization of the tooth surface which may lead to progressive loss of tooth structure and associated pain and morbidity (Selwitz et al, 2007¹). The development of caries lesions involves a net mineral loss of dental tissue, (mediated by the acid in dental bacterial plaque on the surface of the tooth), in what is initially principally a sub-surface phenomenon. Detecting, assessing, diagnosing and treating such hard tissue lesions is a core activity in dentistry. (Pitts NB, 2009²; Fejerskov O, et al 2008³; Paris S, 2013⁴). The main detection and diagnostic aids for caries have long been visual inspection and the use of a probe, together with X-ray images.

[figure not shown]
While a number of technologies have been developed to aid caries lesion detection, this step represents only part of the problem for clinicians in relation to clinical decision-making. Determination of the activity status of a lesion is required in order to assess the treatment needs for this lesion. Current methods of clinical assessment of lesion activity are problematic and involve the clinician's subjective assessment and/or the monitoring of lesion behaviour over time using a specific detection technique such as radiography and/or a combination of factors involved in caries aetiology to produce an algorithm weighted in an attempt to discriminate between active and inactive lesions. The assessment of the activity status of a specific lesion in a single patient visit remains difficult (Ekstrand K et al, 2009⁵; Ekstrand K, Martignon S, 2013⁶) since it currently involves the visual assessment of the subtle differences in the physical characteristics of the lesion surface. Not all dental caries lesions progress to cavitation. The determination of which early 'white spot' lesions will progress can currently only be achieved with any significant degree of accuracy by monitoring over time. Such observing of a lesion risks its progression beyond the stage where preventive interventions are appropriate to a point at which more complex treatments are involved. There are significant differences in the treatment requirements for active and inactive caries lesions, with consequent marked differences in costs and outcomes for the patient, dentist and third-party payer. There is thus a need to develop a technique to aid dentists in identifying the activity status of caries lesions at a single visit in order to optimise the use of non-invasive preventive therapies, as compared to operative / surgical interventions, which tend to be more expensive and can have long-term negative clinical consequences (Qvist V 2008⁷; Longbottom C et al, 2009⁸; Meyer-Lueckel H et al, 2013⁹)

